- III. the implementation of the Levy (anticipated Apr 2018)

Each of these events aim to prompt changes in industry behaviour (primarily reformulation to lower sugar content but also other changes, e.g. in marketing to persuade consumers to switch to lower sugar alternatives). Reformulation (e.g. by Tesco and Britvic) is already occurring. Moreover, each phase of the introduction of the SDIL is accompanied by media coverage orchestrated by HM Treasury, which may emphasize the health risks of SSB consumption. Introduction in April 2018 is also likely to be associated with a rise in the price of SSBs. All of these changes may impact SSB and total sugar consumption, with potential consequences for diet and health. The effects of these 'perturbations' in highly complex food and health systems are multiple and likely to interact dynamically, as illustrated by our 'systems map' (see Appendix A). The outcome of the levy consultation (undertaken in summer 2016)¹⁹ has been published and the amounts of the levy were included in the Finance Bill 2017, which received Royal Assent in May 2017. The current proposal is to impose the levy in relation to the sugar content of drinks as follows:

- No levy on drinks $\leq 5\text{g}/100\text{ml}$ of added sugar
- 18p/L on drinks $>5\text{g}/100\text{ml}$ and $\leq 8\text{g}/100\text{ml}$ of added sugar
- 24p/L on drinks containing $>8\text{g}/100\text{ml}$ of added sugar

Additional components may be announced, which we will consider including within the evaluation. Levy revenue will be used to promote children's health (funding sport and breakfast clubs in school). As this expenditure is guaranteed (i.e. not contingent on SDIL revenue) it will not be considered in this evaluation.

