We will use an in-house, bespoke dataset (developed during our formative work) to assess non-alcoholic drink market diversification, formulation and price. We have developed automated data collection techniques (i.e. 'data scraping') and will use these to collect monthly, time-stamped data on all soft drinks available for purchase from six online UK supermarkets (Tesco, Morrison's, Asda, Sainsbury's, Waitrose and Ocado). Together these supermarkets (online and in-store) represent more than 75% of the UK grocery market.⁴³ The resultant database (FoodDB) contains data on the complete product range of soft drinks from each supermarket in each month.

We will add data from any new online supermarkets that open during the project. Maintenance of FoodDB will be conducted monthly to ensure that the source code that supplies the dataset continues to run appropriately (it also will be necessary to adapt this source code when online supermarkets change their appearance, format or layout).

For each drink we will continue to collect: date of data collection; nutritional content; price; pack size; serving size; whether or not the drink is on promotion; and manufacturer. Complete datasets for all drinks were collected in December 2013 and October 2016. Data from 1281 Tesco drinks were collected from 2011 to 2016 using a combination of live and archived websites, 391 of which have more than three time points at which data was available. Full monthly data on all drinks from all six major online supermarkets is available from October 2016.

Outcome measures

We will have three outcome measures, one related to each of market diversity, formulation and price:

- number of products (e.g. Coca-Cola, not Coca-Cola 500ml bottle) available across six online supermarkets per month (market diversity)
- mean total sugar concentration in g/100ml per month (formulation)
- mean price (not sales-weighted) in £/100ml per month (price)

These will be considered overall and in each of the four drinks categories described above separately.

Study period and sample size

As described above we have some FoodDB data from 2013, with full data available from October 2016. This study will, therefore, include data from October 2016 (6 months after intervention announcement) – April 2020 (2 years after intervention implementation).

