Data are available per calendar month, thus providing 12 time points/year from full establishment of FoodDB onwards (October 2016), and a total of 42 time points in the study. Currently, we estimate that more than 1000 unique soft drinks products will be included per time point. This dataset therefore substantially exceeds current recommendations for minimum samples sizes for ITS analyses of at least 10 time points before and after the intervention, and at least 100 observations per time point.

Data analysis

We will conduct single time point, ITS analyses for each outcome overall in each of the four drinks categories described above separately. The unit of analysis will be the calendar month. As data is only available from after intervention announcement to after intervention implementation, we will include only one 'intervention' point – intervention implementation.

As FoodDB is a database of products, rather than purchases or consumption, it will not be possible to study any differences by socio-demographic characteristics of purchases or consumers. Additional analyses stratified by supermarket price point may be possible e.g. as a student project add-on.

Study 1b: The impact of the SDIL on purchases of drinks, confectionery and toiletries; overall and by age, sex & SEP

Study design

Using commercial data on household purchasing, we will use ITS methods to study whether the announcement or implementation of the SDIL was associated with changes in level or trend of purchasing of drinks in the four categories described above. Inclusion of all four categories will allow us to explore substitution between drinks categories. We will study changes in confectionery purchases to explore substitution to another high-sugar category. Throughout we will use purchasing of toiletries as a 'non-equivalent' comparator that is likely to be effected by income and spending, but not the SDIL. We will study effects across total volume (l or kg), total value (£) and total sugar content of products. Whilst the SDIL aims to reduce consumption of added sugars, levy bands are expressed in terms of total sugars as this is the data that most producers have available to them and which is also available in the KWP dataset. We will study effects overall, and whether there are any differences in effect by household socio-demographics – householder age, household composition and size, and occupational social class.

Data source

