For this project, we will further develop the PRIMEtime model in five ways. First, we will build the first part of the model that estimates changes in soft drink risk as a result of the SDIL, based on results drawn from elsewhere in this project. Here, the inputs will be changes in consumption of sugar drinks (from the interrupted time series analysis of the Kantar World Panel dataset) and changes in average sugar levels in sugar drinks (from the interrupted time series analysis of the foodDB dataset), which will provide population-level estimates that can be converted into changes in ‘equivalised sugar drink consumption’.

Second, we will adapt the existing model to incorporate dental caries, using the datasets described above. Third, we will extend the PRIMEtime model to incorporate children and adolescents who are high consumers of soft drinks by using age and sex-specific estimates of soft drink consumption derived from the NDNS. This will require us to make assumptions regarding how overweight and obesity tracks from childhood into adulthood, which will be informed by the literature. We will conduct sensitivity analyses to test how sensitive our results are to these

changes. However, with the exception of T2DM we do not anticipate that these assumptions will have a big influence on the results as the cardiovascular disease and cancer outcomes that are linked to overweight status in the model do not occur until old age, which for children will not occur for many decades when the model results will be heavily discounted.

Fourth, we will explicitly model lag times between changes in soft drink consumption and health outcomes, with reference to models that have explored time lag between dietary change and health.⁶⁶ The assumptions around time lag will be tested in sensitivity analyses. Fifth, we will re-parameterise the model for the whole UK (currently the model is parameterised for England) using data on health statistics from the Office for National Statistics, the General Register Office for Scotland, the Northern Ireland Statistics and Research Agency and UK results from the Global Burden of Disease study.

Study populations & data sources

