The results from the health model will compare health outcomes in the UK in a baseline scenario where the three stages of implementation of the SDIL (see above) are introduced with a counterfactual scenario where the SDIL is not introduced. Sensitivity analyses will explore scenarios when the early stages of the implementation are introduced without the final implementation of the levy. The data sources that will be used to parameterise the model are described above.

Proposed outcome measures

We will model key health outcomes over medium and long term time horizons, simulating a cohort representing children, adolescents and adults in the UK. The model will estimate the change in dental caries, obesity and T2DM (and associated long term health conditions including cardiovascular disease and renal disease) as a result of age and sex specific estimates of soft drink consumption and average sugar levels in soft drinks. Modelling results will be stratified by socioeconomic groups, to provide estimates of the impact of the SDIL on health inequalities.

The PRIMETIME model will produce outcomes over the medium term (up to 10 years) and long term (>10 years), explicitly accounting for time lag between implementation of the three phases of the SDIL, system change and subsequent changes in health. Sensitivity analyses will explore the effect of applying discount rates to future events. We will use a discount rate of 1.5% as recommended by NICE for evaluations of public health interventions (NICE, 2012).

The outcomes will be changes in the following:

- Medium and long term change in prevalence of dental caries, overweight and obesity
- Change in incidence of T2DM over the medium and long term
- Change in incidence of cardiovascular and kidney diseases and cancers in the medium and long term
- Change in years of life lost due to early mortality from any condition
- Change in quality adjusted life years (QALYs) lost or gained.

Data analyses

We will estimate 95% uncertainty intervals around all of the outcomes, based on Monte Carlo analyses that will sample from distributions around each of the model parameters included in the analysis (e.g. the relative risk estimates associated with dietary change and health outcomes; the effect size of the intervention etc.) Since the PRIMETIME model only includes risk parameters that are statistically significant at a 5% level, it follows that the uncertainty associated with the diet-

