14.1 Appendix A: System map

14.2 Appendix B: Data table

	System map factor with measurement available	Data type	Data source	Work Package	Cost for access	Cost for collection
Industry Actions	Reformulation of sugar in existing products and role of retailers	Commercial sales data	Kantar WorldPanel	WP1	Yes	No
	Product and brand change - diversification, innovation	Supermarket inventory data	Online supermarket websites	WP1	No	Yes
	Price of other products	Supermarket inventory data	Online supermarket websites	WP1	No	Yes
	Price of SSBs	Supermarket inventory data	Online supermarket websites	WP1	No	Yes
	Other defensive tactics (i.e. industry lobbying)	Industry communications and interviews	Industry online publications and stakeholders	WP4	No	No
Consumer Behaviour	Purchasing of SSBs	Commercial sales data	Kantar WorldPanel	WP1	Yes	No
	Purchasing of other products (substitution, complementing, other)	Commercial sales data	Kantar WorldPanel	WP1	Yes	No
	Taste and preference and public attitudes for SSBs and sugar	Commercial sales data	Kantar WorldPanel	WP1	Yes	No
	SSB consumption	National Survey	National Diet and Nutrition Survey	WP1	No	No
	Total sugar consumption	National Survey	National Diet and Nutrition Survey	WP1	No	No
	Whole diet composition	National Survey	National Diet and Nutrition Survey	WP1	No	No
	Acute and chronic health and wellbeing outcomes	Administrative data, national study and PRIMETIME model estimates	Hospital Episode Statistics (dental caries); National Child Measurement Programme (childhood adiposity); Office for National Statistics and the General Register Offices for Scotland and Northern Ireland and Hospital Episode Statistics (model)	WP1 & WP2	No	No
Public Acceptability and Discourse	Media, political and public discourse on SSBs and sugar	News media coverage, social media, documentation and online sources	LexisNexis, Twitter, Parliamentary records and documents and online media	WP4	No	No
	Acceptability of types of intervention	Focus groups	General public including parents, children and young adults	WP4	No	Yes
	Emerging evidence for importance of SSB taxes	Interviews	Professional stakeholders	WP4	No	Yes
Government Actions	Chancellor's announcement	Documentation	UK Treasury	WP1-5	No	No
	Consultation	Documentation	UK Treasury	WP1-5	No	No
	Legislation passed	Documentation	UK Treasury	WP1-5	No	No
	Industry levy	Documentation	UK Treasury	WP1-5	No	No

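### WP2 takes its sugar-content effect from a time series that starts after the announcement and models only implementation, yet uses it to compare the whole levy with no levy

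*Protocol*

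**What the plan says.** **Study 1a (Protocol 7.1).** The window is set as follows: "This study will, therefore, include data from October 2016 (6 months after intervention announcement"), running to two years after implementation, with "a total of 42 time points in the study". The reason for the single break is "As data is only available from after intervention announcement to after intervention implementation", and so "we will include only one 'intervention' point – intervention implementation".

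**General WP1 analysis text (7.1).** In an uncontrolled interrupted time series (ITS), the comparator is the regression line from the preceding period. The same text promises announcement and implementation effects for each outcome at 12 and 24 months.

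**WP2 inputs (7.2, Proposed methods).** Two inputs are named. One is the change in consumption, from the KWP time series. The other is "changes in average sugar levels in sugar drinks (from the interrupted time series analysis of the foodDB dataset").

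**WP2 contrast (7.2, Study populations & data sources).** All three stages of the levy are compared with a "counterfactual scenario where the SDIL is not introduced". Sensitivity scenarios keep the early stages and remove final implementation.

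**Background (4.1).** Each of the three events, including the announcement, is meant to prompt industry change, mainly reformulation. The section adds: "Reformulation (e.g. by Tesco and Britvic) is already occurring".

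**Appendix B (14.2).** The row "Reformulation of sugar in existing products and role of retailers" names Kantar WorldPanel as its source. Supermarket websites, the source of FoodDB, are listed for product diversification and price.

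**The concern.** The effect that Study 1a estimates is not the effect that WP2 needs. Study 1a measures the departure at April 2018 from a trend that already contains the response to the announcement. WP2 needs the distance from a world in which the levy was never announced. The two agree only if little or no reformulation came before implementation, and section 4.1 says otherwise.

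Reformulation is the response that the protocol treats as the levy's main aim. If much of it came early, the WP2 formulation input could be too small, zero or of the wrong sign. The health part of WP3 would inherit this, because section 7.3 builds it on the WP2 model. The early-stages-only scenario has no usable formulation input at all, since Study 1a estimates no announcement effect.

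**Working it through.** **1. The plan's own count.** October 2016 to March 2018 is 18 months and April 2018 to March 2020 is 24 months: 18 + 24 = 42, as stated (43 if April 2020 is also counted). None of the 42 precedes the announcement. April to September 2016 (6 months) lies outside the series.

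**2. What the planned model returns.** Set the true total fall in sugar content due to the levy to 1. Let a share *s* occur before April 2018 and the rest, 1 − *s*, at implementation, with content flat afterwards and no other trend. The shares and shapes are assumptions.

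*Case A: linear from April 2016 to April 2018.*
- The line fitted to the 18 months has slope −*s*/24 per month and reaches −*s* at April 2018.
- Projected *h* months on, it stands at −*s*(1 + *h*/24). The observed level is −1.
- Share of the true effect returned: R(*h*) = 1 − *s*(1 + *h*/24).

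*Case B: all of s completed before October 2016.*
- The fitted line is flat at −*s*, so R = 1 − *s* at any *h*.

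*Case C: linear from October 2016 to April 2018.*
- The slope is −*s*/18, so R(*h*) = 1 − *s*(1 + *h*/18).

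| *s* | A, 12 mo | A, 24 mo | B, 12 and 24 mo | C, 12 mo | C, 24 mo |
|---|---|---|---|---|---|
| 0% | 100% | 100% | 100% | 100% | 100% |
| 25% | 62.5% | 50% | 75% | 58% | 42% |
| 50% | 25% | 0% | 50% | 17% | −17% |
| 75% | −12.5% | −50% | 25% | −25% | −75% |

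A negative entry means that the model reports a rise in sugar content attributable to the levy. Fitting the segmented regression to noise-free data gives the same values.

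**3. The same truth with a pre-announcement series.** I used 72 months from April 2014 with breaks at April 2016 and April 2018, and measured the effect from the pre-announcement line. The model recovers 100% at 12 and 24 months in every case above. The months stand in for KWP's 6 × 13 = 78 four-weekly periods. This check shows the absence of bias under these assumptions and says nothing about precision.

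**4. Sections side by side.** The input (7.2, Proposed methods) is an implementation-only estimate, while the contrast (7.2, Study populations) is all stages against none. Appendix B assigns reformulation to KWP, and section 7.2 assigns it to FoodDB. Section 7.1 admits that the Study 1a series is short, but no section carries that limit into WP2.

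**The case against.** The strongest reply is that Study 1a is described honestly. Its stated aim concerns implementation, the short series is disclosed, and the single break is explained. That stands: the fault is in the WP2 input line, not in Study 1a. It is also true that Study 1b already models total sugars in purchased drinks with both breaks, and that Study 1c covers sugar consumption from 2008. Neither shares the defect, so the evaluation as a whole does not lose the sugar effect.

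A reader might infer several stronger things that the documents do not support:

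- **That there are no FoodDB data before the announcement.** Section 7.1 records a complete collection in December 2013 and partial single-retailer data for 2011 to 2016. They are left out of the planned series.
- **That WP2 counts a reformulated drink twice, as lost sugary volume and again as lower mean sugar.** That requires levy-eligible volume to be paired with a mean over all drinks. Section 7.2 uses soft drinks for both inputs in one place and sugar drinks for both in another, and the conversion method is in a cited source not available here.
- **That every WP2 and WP3 result scales with this input.** KWP volume is a separate WP2 input, and WP3 also covers levy revenue, price pass-through and sector effects.
- **That the unweighted product mean biases the result in a known direction.** Lack of sales weighting is stated only for price. For sugar it follows from FoodDB holding products rather than purchases. The error could go either way, depending on whether leading or minor products reformulate.

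**Conclusion.** The point holds as a mismatch between the WP2 input and the WP2 contrast. An estimate of the change at implementation, measured against an already exposed period, is used as the effect of the whole levy. It cannot supply the planned early-stages scenario, and it conflicts with Appendix B.

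The size is conditional. In the cases tried, the planned input is unbiased only when no reformulation precedes implementation. With a quarter of the fall occurring early, it returns 42% to 75% of the truth at 24 months. With half, it returns −17% to 50%, and with three-quarters, −75% to 25%. These figures assume flat content after April 2018 and no trend unrelated to the levy. The early shares are mine, because the protocol gives none.

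**What to change.** **Change the WP2 input line in section 7.2.** Take the formulation input from the KWP time series: total sugars and litres of soft drinks on one common denominator, April 2014 to March 2020, with both breaks. State explicitly that the total effect is projected from the pre-announcement trend. The general rule in 7.1, which uses the preceding period, would otherwise bring the same problem back at the second break. The announcement segment can then inform the early-stages scenario.

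**Keep FoodDB as product-level evidence.** Label it as change at implementation and use the December 2013 collection as a descriptive anchor. Align section 7.2 with Appendix B.

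**Minimum alternative.** If FoodDB stays as the input, restrict WP2's formulation claim to the implementation increment and drop the early-stages scenario for formulation.

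**Cost.** No new data are needed, as Study 1b already plans litres and total sugars by category. WP2 model preparation is due by September 2021, so data collection is unaffected.

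**Limits to state:**
- Purchase-weighted sugar concentration mixes reformulation with consumer switching.
- KWP nutrition data may lag behind reformulation; FoodDB can check this from October 2016.
- The main panel misses out-of-home purchases. Section 7.1 puts purchases for immediate consumption at about one-third of soft drink purchases, and the on-the-go panel has only 7 months before the announcement.
- Two pre-announcement years (2 × 13 = 26 periods) are projected up to four years ahead, so the interval should carry that uncertainty.

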7.2 WP2 – Impacts on medium to long term health outcomes

Study design

To estimate the impacts of the SDIL over longer time horizons, we will simulate a range of outcomes using a proportional multistate life table approach, adapting an existing life table model (PRIMEtime).⁵⁹ The results from WP1 will be used to estimate effect sizes in terms of sugary drink consumption and free sugars from drinks. The PRIMEtime model will then estimate the impact of these changes on health outcomes over the medium term (next 10 years), and long term (>10 years).

Proposed methods

The health model will use a proportional multi-state life table approach.⁶⁰ It will be parameterised with data on disease incidence and mortality in the UK taken from the Office for National Statistics, linked datasets of HES and death certificates and disease registries. The diseases in the health model will include dental caries, T2DM, cardiovascular diseases, kidney disease and obesity-related cancers (i.e. cancers of the colon, kidney, liver, breast and pancreas). The results of WP1 will determine the change in mean soft drink consumption (ml/day) and the mean sugar concentration of soft drinks (g/ml). Using a method that we have previously developed to estimate the potential impact of the SDIL under different implementation scenarios⁵⁵, we will convert these outputs into measures of ‘equivalised sugar drink intake’. These changes will be translated into changes in body weight using bespoke meta-analyses of the effect of sugar drink consumption on body weight in both adults and children. For an overview of the trial literature on sugar drink consumption and body weight, see Schillinger et al. (2016).⁶¹ Changes in body weight will be translated into the health outcomes by estimating population impact fractions (PIFs), similar to methods used by the Global Burden of Disease project⁶². The PIFs will be based on hazard ratios linking body weight and the health outcomes, which will be drawn from meta-analyses of prospective cohort studies (e.g. Prospective Studies Collaboration, 2009; WCRF/AICR, 2007). For T2DM, we will model the health impact between soft drinks and disease outcome directly using results from prospective cohort studies.^{59 63} For dental caries we will model the impact between sugar consumption and disease outcome using results from a prospective cohort study.⁶⁴ Work has recently been completed to apply disease utility weights to the PRIMEtime model using a comparable study of population-based EQ-5D scores for the US population adapted for the UK by using UK-based time trade-off tariffs.⁶⁵

For this project, we will further develop the PRIMEtime model in five ways. First, we will build the first part of the model that estimates changes in soft drink risk as a result of the SDIL, based on results drawn from elsewhere in this project. Here, the inputs will be changes in consumption of sugar drinks (from the interrupted time series analysis of the Kantar World Panel dataset) and changes in average sugar levels in sugar drinks (from the interrupted time series analysis of the foodDB dataset), which will provide population-level estimates that can be converted into changes in ‘equivalised sugar drink consumption’.

Second, we will adapt the existing model to incorporate dental caries, using the datasets described above. Third, we will extend the PRIMEtime model to incorporate children and adolescents who are high consumers of soft drinks by using age and sex-specific estimates of soft drink consumption derived from the NDNS. This will require us to make assumptions regarding how overweight and obesity tracks from childhood into adulthood, which will be informed by the literature. We will conduct sensitivity analyses to test how sensitive our results are to these

changes. However, with the exception of T2DM we do not anticipate that these assumptions will have a big influence on the results as the cardiovascular disease and cancer outcomes that are linked to overweight status in the model do not occur until old age, which for children will not occur for many decades when the model results will be heavily discounted.

Fourth, we will explicitly model lag times between changes in soft drink consumption and health outcomes, with reference to models that have explored time lag between dietary change and health.⁶⁶ The assumptions around time lag will be tested in sensitivity analyses. Fifth, we will re-parameterise the model for the whole UK (currently the model is parameterised for England) using data on health statistics from the Office for National Statistics, the General Register Office for Scotland, the Northern Ireland Statistics and Research Agency and UK results from the Global Burden of Disease study.

Study populations & data sources

The results from the health model will compare health outcomes in the UK in a baseline scenario where the three stages of implementation of the SDIL (see above) are introduced with a counterfactual scenario where the SDIL is not introduced. Sensitivity analyses will explore scenarios when the early stages of the implementation are introduced without the final implementation of the levy. The data sources that will be used to parameterise the model are described above.

Proposed outcome measures

We will model key health outcomes over medium and long term time horizons, simulating a cohort representing children, adolescents and adults in the UK. The model will estimate the change in dental caries, obesity and T2DM (and associated long term health conditions including cardiovascular disease and renal disease) as a result of age and sex specific estimates of soft drink consumption and average sugar levels in soft drinks. Modelling results will be stratified by socioeconomic groups, to provide estimates of the impact of the SDIL on health inequalities.

The PRIMETIME model will produce outcomes over the medium term (up to 10 years) and long term (>10 years), explicitly accounting for time lag between implementation of the three phases of the SDIL, system change and subsequent changes in health. Sensitivity analyses will explore the effect of applying discount rates to future events. We will use a discount rate of 1.5% as recommended by NICE for evaluations of public health interventions (NICE, 2012).

The outcomes will be changes in the following:

- Medium and long term change in prevalence of dental caries, overweight and obesity
- Change in incidence of T2DM over the medium and long term
- Change in incidence of cardiovascular and kidney diseases and cancers in the medium and long term
- Change in years of life lost due to early mortality from any condition
- Change in quality adjusted life years (QALYs) lost or gained.

Data analyses

We will estimate 95% uncertainty intervals around all of the outcomes, based on Monte Carlo analyses that will sample from distributions around each of the model parameters included in the analysis (e.g. the relative risk estimates associated with dietary change and health outcomes; the effect size of the intervention etc.) Since the PRIMETIME model only includes risk parameters that are statistically significant at a 5% level, it follows that the uncertainty associated with the diet-

disease risk relationships generate uncertainty intervals that do not cross zero (uncertainty intervals tend to be in the region of 5% to 10% of the outcome measure). This uncertainty will increase with incorporation of uncertainty around the effect size of the intervention, but it is not possible to estimate the final amount of uncertainty before the earlier work packages are completed. We will present the results of the uncertainty analyses in tornado plots, which demonstrate how much of the uncertainty is due to the different model parameters.

We will assess the validity of the model results in a number of ways, following published frameworks for assessing model validity.⁶⁷ We will conduct rigorous unit testing on all model features to ensure internal consistency. We will run the model with extreme values to assess the model logic is appropriate and well-applied in the model framework. Where possible, we will compare the short term results of the model with external datasets collected for this project (e.g. hospital episode statistics for dental caries; national childhood measurement programme results for childhood obesity). And we will compare our model with other models that have assessed the health impact of dietary interventions.

7.3 WP3 – Economic impacts on food and other industries, HM treasury, health and social care

Study design

We will undertake a comprehensive economic assessment of the SDIL that integrates evidence from the other WPs to produce both micro- and macro-economic assessments. As indicated in our earlier work developing a systems map related to the SDIL [NIHR PHR RFS 16-49-01], the implementation and impact of a SDIL may be widespread and diffuse, entailing multiple feedback effects directly from the SDIL, or via impacts on health status, across the health sector, food industry, other government departments, other sectors (such as leisure and retail) and consumer behaviour, with impacts on population health being reinforced or diminished through these broader effects. This requires analysis of both micro-level impacts together with the broader macro-economic context within which these impacts take place.

Micro-economic analysis: will focus upon an assessment of the healthcare cost impacts associated with the SDIL, and in combination with health outcome estimates from WP2, will generate an assessment of cost-effectiveness of the SDIL from the health sector perspective. However, as the direct implementation costs of the SDIL will not fall on the NHS this analysis will also consider cost impacts on the food industry, consumers and other sectors, linking with WP1 and WP4, and feeding in to the macro-economic analysis and a societal perspective.

Macro-economic analysis will encompass these wider impacts of SDIL across industry, households and HM Treasury especially. Through a dynamic assessment of the diffusion of the impact of the SDIL through the broader UK economy, including indirect impacts through changes in health status from WP3, this analysis will identify and quantify the overall macro-economic impact, and disaggregated impacts by sector, socio-economic status and geography, to the UK providing a more holistic assessment of net change and specific areas of economic gain and/or loss.

Proposed methods

Micro-economic analysis: Micro-economic analysis will focus specifically on the health and social care sector, and examine other specific impacts which will provide the wider context of impact across the announcement and implementation phases of the SDIL and be used to feed in to the macro-economic assessment outlined below.

With respect to the health and social care sector, the PRIMETIME model (WP2) will provide predictions of the core medium- and long-term health impact of the SDIL across a number of health conditions (see description of WP2). This model will form the basis for a micro-economic model through adaptation to incorporate key cost nodes specifically for health and social care services. NHS costs will be estimated using programme budgeting data and Hospital Episode Statistics, with adjustments for specialised services and primary care expenditure.⁶⁸ Social care and wider societal costs will be implemented using methods developed by the University of York and the Department of Health,⁶⁹ and are based on a regression analysis estimating the probability of needing residential care by age and quality of life with adjustments for those with dementia and stroke. Analysis will extend the PRIMETIME model to incorporate dental caries and associated health care costs, as well as cost estimates to cover children and adolescents. We will further develop UK-specific cost estimates alongside the model being extended for wider UK health application (the PRIMETIME model is currently parameterised for England only). This model will allow assessment of the costs (or most likely savings) accrued to the NHS and social care from a reduction in SSB consumption and QALY impact from the SDIL. Given that the implementation cost of SDIL do not fall on NHS budgets, it is expected that this will be a dominant intervention – cost saving and outcome enhancing – but we will be able to determine the extent of this and identify where these savings may fall; and if there are any costs accruing elsewhere in the profile of ICD-10 and HES data (e.g. higher level of accidents due to increase physical activity programmes).

With respect to the wider economic impact on specific sectors and population groups, we will work closely with WP1 and WP4. WP1 utilises Interrupted Time Series (ITS) analysis to estimate impacts of the SDIL to estimate causal impact of the SDIL across the system previously specified (Appendix A). The core data is focussed on expenditures on SSB products and the levy/price impact associated with demand changes. The data will provide diverse information on (re)formulation, promotional activities, actual prices, purchases and consumption of SSBs to provide estimates of early health impacts (dental caries, obesity – WP2 will extend this in breadth and depth). Additionally the data allow analysing substitution effects towards confectionery. This considerable depth of analysis of the primary industry will be supplemented through work in WP3 estimating financial impact more broadly across critical sectors of the economy based on corporation financial reports (e.g. on product mix, product pricing, revenues per product stream etc.) and government statistics (e.g. on sector employment, growth and tax receipts, and spending across education). We will work with WP4 in their qualitative interrogation of impacts and responses from groups such as consumers, retail and manufacturing to focus on the economic impacts that have or are likely to result. This information will form a portfolio of observed and likely economic impacts across the range of core areas identified in our systems map (Appendix A). Work with WP4 will also inform the specification of scenarios to model in both micro- and macro-economic analyses of possible future impacts of SDIL under different contexts.

Macro-economic analysis: We will use the Computable General Equilibrium (CGE) approach to build a mathematical model of the UK economy. This approach is based on micro-foundations, specifying all sectors of the economy and incorporating international trading relationships thus linking the UK within the global context. The micro-foundations enable it to indicate impacts across sectoral, demographic and spatial areas of interest. It also enables it to utilise data such as that gathered above to increase sensitivity to critical factors of relevance, but set within the broad macro-economy. Our CGE approach has been developed over several years to uniquely integrate the core economic model with modules that replicate the core demographic and epidemiological variables of concern to ensure that feedback effects between these areas are integrated in a fully

dynamic assessment.^{70 71} Based on this previous work, we will construct a fully integrated dynamic model for a system-wide evaluation of the SDIL.

In brief, a CGE model is a mathematical model of the whole economy that includes the cost minimising and profit maximising behaviour of producers, consumption and saving behaviour of households and government, taxation mechanisms and the use of labour, capital and other factors in order to produce goods and services for investment or consumption, and includes trade across international borders.^{72 73} The model produces a benchmark solution (representing the current economy going forward on its current trajectory), which is then compared with alternatives incorporating policy change or other events/shocks simulated by the model; in this case various scenarios encompassing a SDIL. Counter-factual solutions based on these scenarios are then compared with the original benchmark (and each other) to estimate the economic impact of the simulated event overall (eg on GDP, employment and inflation), specific sectors (eg SSB manufacturers, retail or leisure), and population groups (eg household by SES).

